Co-investigators:	
• [name] - Director of the Complex Structure Unit 1 Orthopaedics and Traumatology, Città della Salute Hospital / CTO of Turin, Italy.• [name] - 1st level Medical Director of Unit 1 Orthopaedics and Traumatology, Città della Salute Hospital/CTO of Turin, Italy and Cardinal Massaia Hospital, Asti, Italy.
Sponsor contact person:	[name] – Clinical Research Manager at Permedica S.p.A.
Study rationale	The clinical evidence for outcomes after primary total knee arthroplasty with vitamin E polyethylene is still scarce in the short term and published clinical studies on vitamin E polyethylene total knee arthroplasty with medium term results are lacking.
Objective	The aim of the study is to investigate on the survival rate and mid-term clinical and radiographic results of a consecutive series of primary total knee arthroplasty performed using a cemented total knee prosthesis with a mobile insert in polyethylene with vitamin E, comparing them with the same implant with a mobile insert in conventional polyethylene.

Primary endpoint	Cumulative implant survival with revision for aseptic loosening as the end-point.
Secondary end-points	Cumulative implant survival with revision for any reason as the end-point. Reinterventions and non-surgical complications Forgotten Joint Score (FJS-12). America Knee Society Score (Knee / Function). Radiographic signs of radiolucencies and osteolysis.
Study group	Minimum 152 total knee arthroplasties with vitamin E polyethylene insert.
Control group	Minimum 152 total knee arthroplasties with the same implant but with conventional polyethylene insert without vitamin E.
Medical device	GKS Prime Flex Mobile Bioloy, cemented TiNbN-coated mobile bearing knee prosthesis by Permedica with vitamin E polyethylene (VitalE®) or conventional polyethylene rotating ultra-congruent tibial insert.
Inclusion criteria	
 Patient who received primary total knee arthroplasty with GKS Prime Flex Mobile Bioloy by Permedica with vitamin E polyethylene or conventional polyethylene insert. Minimum follow-up of 7 years. Patient aged \geq 18 years and $<$ 85 years. Patients who signed the informed consent.
Exclusion criteria	
 Patient who received knee prosthesis different from Permedica's GKS Prime Flex Mobile Bioloy. Patients already included in other clinical investigations. Patients who do not sign the informed consent.
Telephone contact	Telephone contact of all eligible patients for recording FJS-12, any adverse events, if lost to follow-up or deceased and for scheduling the follow-up visit.
Follow-up visit	Physical examination, AKSS compilation, FJS-12, recording of complications, adverse events, radiographic assessment for periprosthetic radiolucent lines and osteolysis.

2. Introduction and state of the art

One of the most limiting factors for the longevity of a prosthetic implant in hip and knee arthroplasty is the resistance to wear and degradation of the polyethylene acetabular inserts.

The degradation of ultra-high molecular weight polyethylene (UHMWPE) is that process whereby there is an alteration of the chemical structure of the material with a decrease in the molecular weight. Degradation decreases the mechanical characteristics of the polyethylene and, therefore, potentially reduces the longevity of the polyethylene joint insert. Degradation occurs when the polymeric material is exposed to a quantity of energy greater than that of the chemical bonds of which the polymer chains are made up, so that some chemical bonds are broken. and new free radicals are created. This process in the presence of oxygen is called oxidative degradation or more simply oxidation. Once triggered, the oxidative process is irreversible and self-sustaining with the formation of new radicals that react with oxygen, thus creating a chain reaction.

In orthopaedics, polyethylene acetabular inserts are typically subjected to high doses of energy in the form of irradiation with the aim of increasing the degree of cross-linking or sterilizing the device. This radiation, through the splitting of bonds within the polymer chains, produces the formation of active free radicals within the material. Most free radicals recombine, forming new bonds in the amorphous phase of polyethylene, i.e. cross-linking. The free radicals formed inside the crystalline phase remain trapped for a long time and are responsible for oxidation [1-3].

Stabilization with vitamin E

A solution to the problem of oxidative degradation is the addition of doping substances stabilizing against free radicals to UHMWPE. Stabilization of UHMWPE by the addition of vitamin E was introduced in 2005-2006 as an alternative method to annealing and re-melting, to provide greater resistance to oxidation without sacrificing the mechanical properties of UHMWPE. Vitamin E (alpha-Tocopherol) is in fact a natural molecule and is also present in our metabolism as an antioxidant agent. Vitamin E in its synthetic form is added in low concentrations to UHMWPE as a stabilizing agent against oxidative degradation.

Vitamin E would have the advantage of maintaining the chemical and physical properties of the starting raw material over time, therefore prolonging the longevity of the joint component by reducing the risk of breakage, delamination and wear, a risk that increases exponentially with the increase in the degree of oxidation.

The addition of low concentrations of Vitamin E has proven effective in protecting UHMWPE from oxidation in vitro. From research [4,5] it has been seen that a concentration of 0.05% by weight of vitamin E is already sufficient to protect UHMWPE from oxidation.

UHMWPE with vitamin E added represents the latest generation of polyethylene for joint components, developed and introduced on the market in 2006 by Biomet, now Zimmer-Biomet (E1®). Polyethylene added with Vitamin E have recently been regulated through the ASTM F2695-07 standard. On the market today there are many UHMWPEs added with vitamin E which however differ in the treatments they receive during the production process (Table 1).

Commercial name	Raw material	Additive method	Irradiation dose	Irradiation method	Sterilization method
E1™ (Biomet)	GUR 1020/1050	Infused	100 kGy	γ-Beam	γ-Beam
Vitamys® (Mathys)	GUR 1020	Blended	100 kGy	γ-Beam	Plasma gas
Vivacit-E® (Zimmer)	GUR 1020	Blended	100 kGy	E-Beam	Eto
Vitelene® (Aesculap)	GUR 1020	Blended	80 kGy	E-Beam	Eto
Vital-XE® (Permedica)	GUR 1020	Blended	60 kGy	E-Beam	Eto
ECiMa™ (Corin)	na	Blended	120 kGy	Cold E-Beam	na
E-MAX™ (Renovis)	GUR 1020	Blended	100 kGy	γ-Beam	Eto

Table 1. Some of vitamin E-stabilized polyethylene brands for articular inserts for joint replacement in 2018.

Vitamin E UHMWPE in the hip

Numerous clinical studies are reported in the literature regarding primary total hip replacement with cross-linked polyethylene inserts added with vitamin E and the most recent ones show results up to 7 years of follow-up [6,7]. All studies report low linear wear, lower than conventional UHMWPE inserts and comparable to HXPE, and above all they show no signs of periprosthetic osteolysis.

Vitamin E UHMWPE in the knee

Numerous preclinical studies have shown the effective efficacy and safety of adding vitamin E to the polyethylene of joint inserts in total knee arthroplasty [8-11].

Simulator wear tests have shown excellent results with polyethylene inserts added with vitamin E [12-14].

However, in the literature there are few clinical studies published on total knee arthroplasty with polyethylene added with vitamin E and all concern short-term follow-up (maximum 3 years) and cross-linked polyethylene, infused with vitamin E by Zimmer Biomet (E1®), Table 2. To date, the 2 retrospective case series studies confirm comparable short-term clinical, radiographic and survival results of prostheses with inserts with vitamin E compared to inserts without vitamin E [15,16]. A study on retrieved implants after an average in vivo period of 1.5 years reported less damage and less signs of wear and lower level of oxidation on Zimmer Biomet E1 inserts [17].

Ref.	Study design	No. cases	FU	Vit. E insert	Prosthetics	Main outcomes	Conclusion
Takemura, 2019 [15]	Comparative retrospective	100 + 100	2	E1 PS Biomet	VanguardPS cemented	ROM, KSS, radiological signs	No differences
Spece 2019 [17]	Retrievals	103 + 63	1.5	E1 PS vs Arcos PS	VanguardPS cemented	Signs of wear, oxidation	Less oxidation in PE with vit. E
Flament 2016 [16]	Case series	163	3.2	E1	Vanguard cemented	Survival, ROM, KSS, radiological signs	95% survival for any reason
Barrack 2013 [18]	Case report	1	2.5	E1	Vanguard CR casehardened	Insert breakage	No oxidation

Table 2. Literature review on total knee arthroplasty with vitamin E stabilized polyethylene. FU, mean follow-up in years.

Study rationale

The international scientific literature is still lacking in clinical studies reporting the safety, performance and effectiveness of the use of polyethylene added with vitamin E in joint inserts in primary total knee arthroplasty. There is therefore still no short-term clinical evidence on the clinical and radiographic results of these prosthetic implants.

Furthermore, nothing has yet been published in the literature on mid-term results in primary total knee arthroplasty with polyethylene insert added with vitamin E. The maximum follow-up reported from clinical studies in total knee arthroplasty is in fact 3 years.

A study that reports the medium-term results of a series of total knee arthroplasties using polyethylene with vitamin E and comparing them with those of an identical insert but made of conventional polyethylene is therefore considered scientifically valid and well-founded.

The present study therefore aims to verify the survival, clinical and radiographic results of a consecutive series of patients undergoing first-time total knee arthroplasty with a polyethylene insert added with vitamin E, comparing them with an identical insert but made of polyethylene standard, at a minimum follow-up of 7 years.

3. Study design

Observational, cross-sectional, comparative, monocentric clinical study with a retrospective cohort. The study is promoted and sponsored by Permedica S.p.A., [name], Italy <https://www.permedica.it/>. The study centre is the Quadrante Orthopaedics Center (C.O.Q.) Hospital, placed in [name] - Italy. Study principal investigator (PI) will be [name]. The study will be conducted by PI and other co-investigators, PI's collaborators of the Orthopaedics Unit at C.O.Q. Hospital in Omegna and external collaborators of the CTO Hospital of Turin, coordinated by [name], Director of the Orthopaedics Unit and Traumatology 1, CTO Hospital of Turin. The study, being observational, will only concern

the collection of data about the patient, his medical history and pathology, his surgery and prosthetic implant and the clinical and radiographic results. The patient will be contacted by telephone and invited to a follow-up visit. Clinical scores will be recorded by the patient and the investigators, radiographic signs will be recorded from preoperative and postoperative radiographs performed at the last follow-up. The study will therefore not require any additional diagnostic or therapeutic services compared to the standard clinical practice. The study will only take into consideration patients who have already undergone total knee arthroplasty at the C.O.Q. Orthopaedics Unit.

4. Study objective

The aim of the study is to verify the survival and mid-longterm clinical and radiographic results of a consecutive series of primary total knee arthroplasty performed using a cemented total knee prosthesis with a vitamin E polyethylene ultra-congruent mobile insert, in comparison to the same implant with a conventional polyethylene same design tibial insert.

4.1 Primary endpoint

The primary objective of the study is to verify that the survival of the prosthetic implant with vitamin E polyethylene is not inferior to the survival of the prosthetic implant with conventional polyethylene. The primary endpoint is therefore the cumulative implant survival, defining revision for aseptic loosening as the endpoint (or failure).

4.2 Secondary endpoints

The secondary objectives of the study are survival for any reason, clinical results and radiographic results, prevalence of complications. Secondary endpoints are therefore:

- Survival of the prosthetic implant with vitamin E polyethylene and with conventional polyethylene, with revision for any reason as the end-point,
- the American Knee Society Score (KSS) with Knee score and Function score,
- the Forgotten Joint Score (FKS-12),
- Number of reinterventions (without any component removal), non-surgical complications and adverse events,
- Periprosthetic radiolucent lines and radiographic signs of periprosthetic osteolysis.

5. Prosthetic device

The medical device under investigation is a cemented bicompartimental knee prosthesis with a rotating tibial plateau, the GKS Prime Flex Mobile Bioloy® by Permedica S.p.A. (Figure 1). The femoral and tibial components are both coated with a titanium-niobium nitride (TiNbN) ceramic coating with 4.5 ± 1.5 microns thickness (Bioloy®). The femoral and tibial component are both cemented. The rotating tibial insert has an ultra-congruent articular surface and is made with

UHMWPE blended with vitamin E (0.1% alpha-Tocopherol), non-cross-linked and sterilized by ethylene oxide (VitaE®), or with conventional non-cross-linked UHMWPE (Figure 2).

Figure 1. Cemented mobile-bearing total knee prosthesis with TiNbN coating, GKS Prime Flex Mobile Bioloy® by Permedica S.p.A.

[figure not shown]

Figure 2. A: UHMWPE blended with 0.1% vitamin E, non-cross-linked and ethylene oxide sterilized (VitaE®) ultra-congruent rotating insert. B: Conventional, non-cross-linked, E-beam sterilized UHMWPE ultra-congruent rotating insert with same design.

6. Study population

The study will concern a consecutive series of patients who underwent primary total knee arthroplasty with the same knee prosthesis at the C.O.Q. hospital in Omegna (VB), Italy, from January 2011 to December 2015 and who will meet all eligibility criteria.

6.1 Study group

At least 152 knees with GKS Prime Flex Mobile Bioloy prosthesis from Permedica with rotating mobile insert with vitamin E polyethylene (VitalE®).

6.2 Control group

At least 152 knees with Permedica GKS Prime Flex Mobile Bioloy prosthesis with rotating mobile insert with conventional polyethylene without vitamin E.

6.3 Eligibility criteria

Inclusion criteria:

- Patient underwent primary implant total knee arthroplasty surgery cemented with GKS Prime Flex Mobile Bioloy prosthesis with mobile insert by Permedica.
- Patient with minimum follow-up of 7 years.
- Patient aged \geq 18 years and $<$ 85 years.
- Patients who signed the informed consent.

Exclusion criteria:

- Patient with knee prosthesis other than Permedica's GKS Prime Flex Mobile Bioloy.
- Patients already included in other clinical investigations.
- Patients who do not sign the informed consent.

7. Study procedure

The study can start only upon the approval of this protocol by the competent Ethics Committee of the study centre and after formal communication of the study centre.

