7.1 Screening

All patients who underwent primary total knee arthroplasty from January 2011 to December 2015 at the Orthopaedics Unit of the C.O.Q. Hospital in Omegna will be identified through hospital database. If deemed eligible according to the inclusion/exclusion criteria, patients will be contacted by telephone by the principal investigator or one of his representatives and invited to take part in the study. If possible, the patient information sheet, the patient's informed consent form and the information on the processing of personal data will be sent by ordinary post or e-mail. The investigator will invite each patient eligible for the study to present themselves at the C.O.Q. Orthopaedics Unit for a follow-up and will be invited to present themselves with all the radiographic documentation in their possession.

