7.2 Enrolment

The principal investigator, or one of his representatives, will explain to the patient the reasons and methods for carrying out the study and provide all the necessary information before enrolment. The patient will be given the Patient Informed Consent form, the Consent to the Processing of Personal Data form. Furthermore, the investigator will be available to provide an adequate response to any questions or concerns expressed by the patient. The investigator will advise the patient to carefully and calmly read the Patient Informed Consent and Consent to the Processing of Personal Data forms and to discuss their contents with their family, friends and doctor before making any decision

in this regard. The patient will give his informed consent by completing and signing the printed Patient Informed Consent and Consent to the Processing of Personal Data forms. From this point on the patient will be considered enrolled in the study.

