7.3 Follow-up visit

At the follow-up visit, an objective evaluation of the operated knee will be carried out, questions will be asked about the patient's current state of health, as well as a radiographic follow-up evaluation will be carried out assessing the last anterior-posterior and lateral knee radiographs compared with the first postoperative radiograph.

If the patient has signed the Informed Consent and the Consent to the Processing of Personal Data, the information requested in the case report forms described below will be recorded.

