8.3 Data entry, analysis and storage

All printed CRFs number 1-7, fully completed and signed in original, must be grouped together in one folder per patient. The original completed CRFs will be stored by the principal investigator in a specific study file, for a period of 15 years at the study centre. A copy of the completed CRFs will be stored by the sponsor in a specific study file, for a period of 15 years at the sponsor facility. Principal investigator and sponsor have the responsibility for data management. The CRF data will be entered by the sponsor into a single electronic database protected by password, which will undergo periodic back-up after each new data entry. The sponsor will have the responsibility for data analysis. At the end of the study, a PDF/A copy of the database file will be stored at the sponsor server and, moreover, will be saved on CD and other external memory and stored at the sponsor facility.

9. Duration of the study

The study will begin following the Ethics Committee approval and after the authorization from the C.O.Q. Management to start the study. A duration of approximately 12 months is estimated for patient screening, telephone contact, follow-up visits and data recording. The study will end with the completion of all the forms required for all enrolled patients. The duration of data entry from the paper CRF format to the electronic database is approximately 1 week but can be carried out at the same time as data collection. An additional 2 months are estimated for data analysis and drafting of the study report.

10. Statistical analysis

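### Signed consent and an undefined 7-year follow-up criterion decide which knees enter the primary survival analysis, and section 10.2 gives no analysis set or censoring rule

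*Combined protocol and SAP*

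**What the plan says.** **Rules that restrict entry.** Section 6.3 (and the synopsis) lists among the inclusion criteria "Patient with minimum follow-up of 7 years" and a signed consent, and excludes "Patients who do not sign the informed consent". Follow-up is not defined. Section 7.2 places enrolment at signature: "From this point on the patient will be considered enrolled in the study". Section 7.3 records the CRF information "If the patient has signed the Informed Consent and the Consent to the Processing of Personal Data". Section 9 adds: "The study will end with the completion of all the forms required for all enrolled patients". The 7-year condition appears only in 6.3 and the synopsis; 7.2 and 7.3 carry only the consent condition.

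**Provisions that expect a wider population.** Section 7.1 identifies from the hospital database "All patients who underwent primary total knee arthroplasty from January 2011 to December 2015". The synopsis has all eligible patients telephoned, partly to establish who is lost or has died. Section 7.4 requires forms in cases of withdrawal, loss, failure and revision, and ties study completion to all patients judged eligible. CRF 7 (section 8.1) records contact, loss, death, and whether and when the implant was revised, to feed a flowchart of the whole study population.

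**The analysis.** The primary endpoint (4.1) is cumulative implant survival, with revision for aseptic loosening as failure. Section 10.2 names Kaplan-Meier with a 95% confidence interval and the log-rank test. It gives no analysis set, time origin or censoring rule, and does not mention death, loss, non-consent or revision for other reasons.

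**The concern.** A patient who died before contact cannot sign, and one who is never traced will not have signed. Under 6.3 neither is eligible, although three other parts of the plan expect such cases. Membership of the survival cohort then depends on what happened to the patient after surgery, which sits badly with a consecutive series.

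Kaplan-Meier does not need this restriction. A knee whose patient died or was lost contributes time, and any revision, up to its last known status. Leaving it out discards that information, and distorts the estimate if such knees are revised more or less often than the rest.

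Because 10.2 is silent, two analysts could include different knees and report different survival from the same data. Events are few: at the planning rates, 152 × 2.8% = 4.3 failures in the control group and 152 × 2.3% = 3.5 in the vitamin E group.

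**Working it through.** **1. The plan's own figure.** Section 10.1 gives survival of 97.2% and 97.7%, a 4% margin, alpha 5% and power 80%. With one-sided alpha and unpooled variance:

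n = (0.972 × 0.028 + 0.977 × 0.023) × (1.645 + 0.842)² / 0.045² = 151.7, rounded up to 152.

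The planned size reproduces and is not in dispute.

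**2. Precision lost by leaving out the deceased.** Assumptions, because the documents give no death rate:
- 7-year failure of 2.8%. This is the control planning rate, taken from 5-year all-cause registry figures and carried to 7 years.
- Constant hazards, so h = −ln(0.972)/7 = 0.00406 a year.
- Death hazard m of 0.02 or 0.04 a year, unrelated to revision.
- Follow-up uniform from 7.3 to 12.3 years, which is the time from a 2011–2015 surgery to the version 02 approval on 14 April 2023.

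Survivors only: SE = √(0.972 × 0.028 / 152) = 1.34 points.

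All knees, censored at death: the share alive at contact is 82% or 68%, so 152 survivors correspond to about 185 or 225 operated knees (N). The Greenwood-type variance is

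Var = (0.972² / N) × [h / (h + m)] × [exp(7(h + m)) − 1].

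| Death hazard | N | SE, all knees | SE, survivors | Revisions dropped with the deceased |
|---|---|---|---|---|
| 2% a year | 185 | 1.26 | 1.34 | 0.6 |
| 4% a year | 225 | 1.18 | 1.34 | 1.4 |

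About 5.9 revisions are expected among the 152 survivors over their full follow-up. All these counts are all-cause; aseptic loosening is a subset, so counts for the primary endpoint would be smaller.

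**3. Possible bias.** Let q be the share of knees missing and r the ratio of their revision risk to that of the included knees. Then observed risk / true risk = 1 / [(1 − q) + q r]. Take a true difference at the margin, 6.8% against 2.8%, or 4.0 points, with q and r assumed equal in both groups:

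| q | r = 0.5 | r = 2 |
|---|---|---|
| 15% | 4.0 × 1.081 = 4.3 points | 4.0 × 0.870 = 3.5 points |
| 30% | 4.0 × 1.176 = 4.7 points | 4.0 × 0.769 = 3.1 points |

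If r = 1 the difference is unchanged. With equal q and r the ratio of risks also stays at 6.8/2.8 = 2.43, so only the absolute difference moves. If r differs by group, both move. At q = 20% the factor for r = 2 is 0.833. Doubled risk among missing vitamin E knees only gives 5.67 − 2.80 = 2.9 points; among missing control knees only, 6.80 − 2.33 = 4.5 points. The distortion can therefore go either way.

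**4. Dependence on the analysis set.** A simulated cohort with assumed 7-year risks of 5% revision, 20% death and 15% loss, all independent, has true survival of 95.0%. Keeping every knee with censoring gives 94.9%. Restricting to patients alive and contactable at the visit gives 95.0%. Keeping early revisions (as 7.4 suggests) but dropping unrevised knees with under 7 observed years (one way to apply 6.3) gives 93.9%. The data are the same; only the rule changes.

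**The case against.** **Much of the machinery already exists.** CRF 7 captures loss, death and dated revision, CRF 6 can draw on medical records or the telephone call, and the consent sentence in 7.3 sits under the follow-up visit and may be meant only for it. This is fair: the data fields are planned. It does not say which knees are analysed, and 6.3 still makes signature a condition of inclusion. Figure 3 and the annexed CRFs are not shown and may describe these patients, but the analysis rule belongs in 10.2.

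**The effect is small and of unknown sign.** This also stands. Deaths unrelated to revision cost only precision if exclusion does not depend on revision status, and the log-rank comparison is essentially unaffected when selection scales both groups alike.

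**Two stronger readings are tempting.**
- A reader might infer that every knee revised before year 7 is excluded, which would force 7-year survival to 100%. Section 7.4 and CRF 7 expressly expect revised implants, so time since surgery is the more plausible meaning. The wording should still rule the other one out.
- A reader might infer that the 7-year rule contradicts the 2011–2015 surgery window. Section 6 defines the population as patients operated "from January 2011 to December 2015 and who will meet all eligibility criteria", so the two conditions are meant to apply together. A shortfall would require an assumed early contact date. The plan gives a duration for screening and data collection but no start date, and start also depends on authorisation by the centre. By the version 02 approval, every knee operated in the window is more than 7 years from surgery.

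**Conclusion.** The point holds in a limited form. A stated entry rule, not just a missing detail, takes knees of deceased, lost and non-consenting patients out of the primary survival analysis. Other sections expect such cases, and 10.2 does not settle the matter.

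The cost that can be illustrated is precision: a standard error of 1.34 points against 1.26 or 1.18, resting on assumed mortality of 2% or 4% a year, constant hazards and a 2.8% all-cause failure risk. Bias is possible but conditional on a different revision risk in the excluded knees. The documents do not allow its direction or size to be determined, and the figures in step 3 are scenarios only. They do not support a claim that the design guarantees a favourable result for vitamin E. The correction is cheap enough to be worth making, and should be made before the analysis.

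**What to change.** - **6.3:** define the 7-year criterion as time from surgery to the data cut-off, whatever the state of the implant or the patient.
- **10.2:** state that the survival analysis includes every knee operated with the study implant between January 2011 and December 2015 that meets the criteria other than consent. Time runs from surgery, and each endpoint revision counts at its date. Censor at death, at last known status or, for the primary endpoint, at revision for a reason other than aseptic loosening.
- **Other outcomes:** apply the visit condition to AKSS and the radiographic evaluation only. Apply the consent condition to those two and to FJS-12, which the synopsis allows by telephone.
- **Terminology:** reconcile eligible and enrolled across 6.3, 7.2, 7.3, 7.4, section 9 and CRF 7.
- **Consent:** use of records without a signed consent needs Ethics Committee agreement, which the documents do not settle. If it is refused, report all screened knees by group and reason for exclusion. Add a sensitivity analysis that assigns a range of absolute revision risks to knees of unknown status, separately by group. Multiples of the observed risk would not do, because they stay at zero in a group with no events.

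Cost: one amendment, one Ethics Committee request that may be refused, and one extra analysis. No visits are added; the database screen and CRF 7 are already planned.
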